### Adverse events

AEs are any unfavourable or unintended events that affect the patients of the study, regardless of the relevance to the treatment. Any AEs are recorded in detail on the case report form (CRF) and include time of occurrence, duration, relevance to the treatment, stopping or continuing of the treatment, and others. Events are defined as serious adverse events (SAEs) if they lead to death, prolongation of hospitalisation, permanent or severe disability, teratogenesis or carcinogenesis, and significant clinical sequela. The occurrence of SAEs will be reported to Peking University Cancer Hospital Ethics Committee within 24 hours of the initial discovery.

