### Treatments

A standard laparoscopic or open distal gastrectomy with D2 lymphadenectomy (including lymph nodes of numbers 1, 3, 4sb, 4d, 5, 6, 7, 8a, 9, 11p and 12a) is performed by two experienced surgeons, according to the Japanese Gastric Cancer Treatment Guidelines 2014 (V.4) and the Japanese Classification of Gastric Carcinoma (3rd English edition).

In the open group, an approximately 20–25 cm incision is made from the falciform process to the periumbilical area. In the laparoscopic group, one 10 mm trocar for the camera is inserted below the umbilicus. Another three 10 mm ports are inserted in the left upper quadrants 2 cm below the left lower rib margins, the right and left flank areas, respectively. One 5 mm trocar is lastly placed on the right upper quadrants 2 cm below the right lower rib margins. Anastomosis is performed using the instrumental method. The specimen was pulled out through a small median incision under the xiphoid (about 6–8 cm).

For those who underwent laparoscopic gastrectomy, the case is required to be converted to open surgery if one of the following happens: confluent lymph nodes with long axis >3 cm, severe or life-threatening intraoperative complications such as intra-abdominal massive haemorrhage, severe organ damage, or other technical or instrumental factors that require conversion to open surgery.

All patients are managed by a standardised clinical pathway after the surgery. Discharge is recommended when the patients have tolerated more than 2 days of soft diet without abdominal pain or fever. All patients start to accept five cycles of oxaliplatin and capecitabine regimens for postoperative adjuvant chemotherapy within 6 weeks postsurgery. Dose reductions or interruptions are allowed to manage potentially serious or life-threatening adverse events (AEs). In cases of oxaliplatin-related neurological AEs, capecitabine can be continued as monotherapy. Oxaliplatin monotherapy is not allowed. Palliative and supportive care are offered as needed for disease-related symptoms.

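### The closed list of SAE criteria omits life-threatening events and new or repeat hospital admission, so such events may not trigger the 24-hour report to the ethics committee.

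*Protocol*

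**What the plan says.** The Protocol, section Adverse events, sets the rule: "Events are defined as serious adverse events (SAEs) if they lead to death, prolongation of hospitalisation, permanent or severe disability". The sentence ends with two more criteria, "teratogenesis or carcinogenesis, and significant clinical sequela". No phrase marks the list as a set of examples, so it reads as complete. The reporting rule follows directly: "The occurrence of SAEs will be reported to Peking University Cancer Hospital Ethics Committee within 24 hours of the initial discovery". All other AEs go on the case report form, with no deadline stated.

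The Treatments section refers to life-threatening events twice. One reason for converting to open surgery is "severe or life-threatening intraoperative complications such as intra-abdominal massive haemorrhage". For chemotherapy after surgery it says: "Dose reductions or interruptions are allowed to manage potentially serious or life-threatening adverse events (AEs".

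The Outcomes section has its own safety endpoint: complications within 30 days of surgery, graded by Clavien-Dindo. It does not use the SAE definition.

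**The concern.** An SAE definition decides which events reach an outside body quickly. Here it leaves out a class of event that the same protocol expects in the operating theatre and during chemotherapy. It also counts a hospital stay only when an existing stay becomes longer. An admission from home is a different event and is not named.

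What is at stake is prompt oversight of patient safety. The 24-hour report is the only fast safety channel that the protocol describes. The monitoring section otherwise provides annual monitoring by the funder and one interim analysis when half of the patients have been randomised.

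**Working it through.** The protocol states no figure on this point, so there is none to reproduce. The check sets the definition against the events that the protocol expects, and then against its other safeguards.

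**Step 1. The five criteria.** (a) Death; (b) a longer hospital stay; (c) permanent or severe disability; (d) teratogenesis or carcinogenesis; (e) significant clinical sequela. No other section adds to these.

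**Step 2. Three cases tested against them.**

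- *Massive intraoperative haemorrhage, controlled, with discharge at the usual time.* Criteria (a) to (d) are not met. Criterion (e) is undefined, so the answer depends on judgement.
- *Readmission for a surgical complication after discharge.* The first stay has ended, so on a plain reading there is nothing to prolong under (b). Criterion (e) may or may not be judged to apply.
- *Admission from home for chemotherapy toxicity, with recovery.* Again there is no current stay to prolong, and only (e) could apply. The protocol does not state the setting for chemotherapy. Oral capecitabine on days 1–14 of each cycle, as described for the preoperative cycles, makes time at home likely; this is an inference.

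In none of the three cases is SAE status assured.

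**Step 3. Does another safeguard close the gap?**

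- *CRF recording.* It captures the event but triggers no expedited report.
- *Clavien-Dindo grading.* It covers 30 days after surgery and triggers no report. Adjuvant chemotherapy starts within 6 weeks of surgery (6 × 7 = 42 days) and has five cycles. The protocol gives a cycle length of 3 weeks for the preoperative cycles only. If it also holds after surgery (assumption), the course lasts 5 × 3 × 7 = 105 days. For a start on day s after surgery, the part outside the 30-day window is 105 − (30 − s) days if s is below 30, and all 105 days otherwise. Even at the unrealistic limit s = 0, that is 75 of 105 days (71%). At s = 42 it is the whole course. The three preoperative cycles fall outside the window as well.
- *Visit schedule.* Data are collected daily only until discharge (Data collection and analysis). Follow-up visits are then every 3 months for two years and every half year in the third.

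None of these gives a prompt report for the cases in step 2.

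**Step 4. Size.** The protocol gives no rate of readmission or of life-threatening events that resolve, so no number of missed reports follows from it.

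**The case against.** The strongest reply is that the gap is narrower than it looks, and much of that reply stands.

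- Many life-threatening events in hospital will lengthen the stay, cause death or leave sequelae, and so qualify already. Criterion (e) is broad enough for an investigator to include others. This is why the claim is only that such events are not guaranteed to qualify.
- Nothing is lost from the record, because every AE goes on the CRF whatever its seriousness.
- The document is a published account of the trial, and a fuller operational definition may exist elsewhere. That cannot be checked here.
- The abstract reports 96 patients enrolled, so most operations are probably past. An amendment cannot create 24-hour reports in retrospect. This bears on the form of the fix and does not remove the defect.

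A reader might go further and infer bias between the arms: the same late complication would be an SAE in a patient still in hospital, but not in one who has gone home, which would favour the arm discharged earlier. The documents do not support this as a finding. The SAE count is not a named endpoint, and the 30-day morbidity endpoint does not depend on discharge. One discharge rule applies to both arms: "Discharge is recommended when the patients have tolerated more than 2 days of soft diet without abdominal pain or fever". The Introduction reports faster gastrointestinal recovery after laparoscopy, but on length of stay it says only that there was no increase. What remains is an unquantified possibility that a descriptive SAE tally could depend on discharge timing.

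A reader might also want a count of unreported events. Any such count would rest wholly on assumed rates, and the events would lack the expedited report without being absent from the data.

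**Conclusion.** The point holds as a defect in a stated safety rule. The SAE list has no criterion for a life-threatening event or for a new or repeat admission, and the protocol itself expects life-threatening events. The clearest gaps are life-threatening events that resolve without a longer stay, and admissions after discharge, including those during adjuvant chemotherapy. These may miss the 24-hour report.

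The conclusion rests on reading the list as closed and on no fuller definition existing elsewhere. It needs no assumed event rate, and its size in events is unknown. It does not touch the primary endpoint, the sample size or the 30-day morbidity comparison, and it does not establish bias between the arms. It should be corrected because it concerns patient safety and the correction is cheap.

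**What to change.** In the section Adverse events, add two criteria to the SAE definition: *is life-threatening* and *requires hospital admission or readmission*. Apply the amended definition to all ongoing treatment and follow-up. Reclassify AEs already on the CRF under the same definition, so that any SAE tally is consistent across patients and arms; a forward-only change would leave two definitions within one trial. Replacing the final conjunction of the list with *or* would be a clerical tidying only.

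The cost is a short amendment, some reclassification work on recorded AEs and a few more expedited reports. No treatment, endpoint, sample size or planned analysis changes.

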### Sample size

Due to the lack of results from previous similar research, a double-criteria approach described in the paper of Neuenschwander *et al* was used to calculate the required sample size in order to identify non-inferiority of laparoscopic versus open gastrectomy in terms of RFS. The first criterion was that the HR estimate was smaller than a critical threshold of 1.12, which corresponded to a difference of 8% in the 3-year RFS between two arms. As suggested by the paper, this number was chosen on the basis of clinical considerations. The second criterion required that the upper estimated one-sided 95% confidence bound of the non-inferiority margin was smaller than 1.59, which was calculated based on prior clinical research on laparoscopic gastrectomy after neoadjuvant chemotherapy, as well as on open gastrectomy after neoadjuvant chemotherapy.

On the basis of this approach, a sample size of 80 (40 per arm) is planned, with a type I error of 0.05 (two-sided) and a statistical power of 80%. The total sample size is 96 (48 per arm) after taking account of a 20% dropout rate in each group. The planned recruitment period is 2 years and the follow-up duration is 3 years.

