## ABSTRACT

**Introduction** Current guidelines recommend open gastrectomy with D2 lymph node dissection and adjuvant chemotherapy as the standard treatment for advanced gastric cancer. However, the prognosis is not satisfactory. Perioperative chemotherapy has been proposed to improve survival. Although still in debate, the efficacy of laparoscopic distal gastrectomy (LDG) in patients with advanced gastric cancer has been demonstrated in a few trials. Therefore, LDG after neoadjuvant chemotherapy can be a candidate for future standard treatment on advanced distal gastric cancer. We propose a randomised phase II trial to compare LDG and open distal gastrectomy (ODG) after neoadjuvant chemotherapy for advanced gastric cancer.

**Methods and analysis** To test the efficacy and safety, a randomised, open-label, single-centre, phase II trial was designed to evaluate the non-inferiority of LDG compared with ODG after neoadjuvant chemotherapy, with 3-year recurrence-free survival as the primary endpoint. The chosen critical value of a non-inferiority margin was an increase of <8%. The study started in 2015 and enrolled 96 patients according to a prior sample size calculation. Intention-to-treat and per-protocol approach will be used for efficacy analysis, and as-treated analysis will be applied for safety analysis. The survival curves will be constructed as time-to-event plots using the Kaplan-Meier method and compared using log-rank tests and Cox proportional hazards model. All statistical analyses will be conducted in standard statistical software with a significance level of 0.05.

**Ethics and dissemination** This study was approved by the Peking University Cancer Hospital Ethics Committee. The results will be submitted for publication in peer-reviewed journals.

**Trial registration number** NCT02404753; Pre-results.

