Intention-to-treat and per-protocol approach will be used for efficacy analysis. As-treated analysis will be applied for safety analysis. For variables with a significant amount of missingness, multiple imputations will be conducted for the purpose of sensitivity analysis. In terms of descriptive analysis, categorical data will be presented as number and percentage. Continuous variable will be presented as mean and SD if normally distributed, or as median and range otherwise. The primary analysis in this study aims to compare the 3-year RFS rate between laparoscopic and open gastrectomy after neoadjuvant chemotherapy. The date of recurrence is defined as the date of all-cause death or when a clinician judges recurrence

considering all information including serum tumour and the results of imageological examination. The RFS curves will be constructed as time-to-event plots using the Kaplan-Meier method. Log-rank tests will be used to make a simple comparison of the survival curves. Cox proportional hazards model will be performed to compare RFS after taking into account potential confounders. The overall survival will also be analysed in the same manner. Subgroup analyses will be conducted by age group, tumour location, body mass index category and TNM stage. All statistical analyses will be conducted in standard statistical software with a significance level of 0.05.

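### A hazard ratio of 1.12 cannot equal an 8-point difference in 3-year RFS: it implies at most 4.2 points, and neither the scale of the 8% nor the control rate is stated.

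*Protocol*

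**What the plan says.** The Sample size section uses two criteria to identify non-inferiority of laparoscopic to open surgery on RFS.

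- The first is that the hazard ratio estimate lies below a "critical threshold of 1.12, which corresponded to a difference of 8% in the 3-year RFS between two arms". The next sentence adds that "this number was chosen on the basis of clinical considerations".
- The second concerns precision: "The second criterion required that the upper estimated one-sided 95% confidence bound of the non-inferiority margin was smaller than 1.59". I read this as the upper bound of the hazard ratio.

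The abstract summarises the margin in one sentence: "The chosen critical value of a non-inferiority margin was an increase of <8" per cent. It does not say what increases or on what scale, and it does not mention 1.59.

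The analysis model is given under Data collection and analysis: "Cox proportional hazards model will be performed to compare RFS after taking into account potential confounders". No section gives an expected 3-year RFS or an expected number of events for either arm.

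**The concern.** The primary endpoint is itself a percentage, the 3-year RFS rate. A difference of 8% between the arms is therefore naturally read as 8 percentage points. A hazard ratio as close to 1 as 1.12 looks too small to produce that.

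If it is too small, the protocol attaches the wrong clinical size to its own threshold. The remark about clinical considerations makes this harder to resolve, because it follows a sentence with two numbers. A reader cannot be sure whether 1.12 or 8% was the clinical choice and which was derived from it.

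A reader who has only the abstract would also take 8% as the loss the trial is designed to exclude. The limit placed on the confidence bound is a hazard ratio of 1.59.

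**Working it through.** **Inputs from the protocol.** Hazard ratio threshold 1.12, equated difference 8%, and upper one-sided 95% bound 1.59 (all Sample size); 96 patients allocated 1:1; Cox model (Data collection and analysis). Control-arm RFS is not given, so a range of 40 to 80% is assumed wherever a rate is needed.

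**Conversion.** With control 3-year RFS equal to S, proportional hazards gives a laparoscopic-arm RFS of S^HR and an absolute difference of S − S^HR.

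**Step 1: try to reproduce the 8% as an absolute difference.** S − S^1.12 is largest where 1 − 1.12·S^0.12 = 0, that is S = 1.12^(−1/0.12) = 0.389. There S^1.12 = 0.347, and the difference is 0.0417. No control rate gives more than 4.17 points, so the 8% does not reproduce.

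**Step 2: find the hazard ratio that 8 points would need.** HR = ln(S − 0.08)/ln(S). Its smallest value is 1.243, at S = 0.409.

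**Step 3: try the relative readings.** At S = 0.50, 0.50^1.12 = 0.460. RFS falls by 0.040/0.50 = 8.0%, and event risk rises from 50% to 54%, also 8.0%. The fall in RFS is exactly 8% at S = 0.499, and the rise in event risk is exactly 8% at S = 0.502. Away from 50% the match is lost.

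| Assumed control RFS | 40% | 50% | 60% | 70% | 80% |
|---|---|---|---|---|---|
| HR 1.12, absolute points | 4.2 | 4.0 | 3.6 | 2.9 | 2.1 |
| 8 points as a multiple of that | 1.9 | 2.0 | 2.2 | 2.7 | 3.8 |
| HR needed for 8 points | 1.24 | 1.25 | 1.28 | 1.34 | 1.47 |
| HR 1.12, relative fall in RFS (%) | 10.4 | 8.0 | 5.9 | 4.2 | 2.6 |
| HR 1.12, relative rise in event risk (%) | 6.9 | 8.0 | 8.9 | 9.8 | 10.6 |
| HR 1.59, absolute points | 16.7 | 16.8 | 15.6 | 13.3 | 9.9 |

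**Step 4: does the mismatch change the verdict?** Use the approximation SE(ln HR) = 2/√events for 1:1 allocation.

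- The 1.12 criterion becomes the stricter of the two only from (2 × 1.645 / ln(1.59/1.12))² = 88 events.
- An 8-point threshold, taken at its smallest hazard ratio of 1.243, would become the stricter only from (2 × 1.645 / ln(1.59/1.243))² = 179 events, more than the 96 patients.
- With 96 patients, complete 3-year follow-up and both arms at RFS of 40/50/60/70%, about 58/48/38/29 events are expected. The largest hazard ratio estimate that then meets the 1.59 bound is 1.59 × exp(−1.645 × 2/√events) = 1.03/0.99/0.93/0.86. All are below 1.12, so the bound decides.
- A simulation (exponential times, 48 per arm, 3 years, 6,000 trials per setting, control RFS 40 to 80%, true hazard ratio 1.00 and 1.59) kept the 1.59 bound and replaced the 1.12 criterion by a difference under 8 points. The verdict changed in at most 0.1% of trials.

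**The case against.** The strongest reply is that 1.12 need not be a miscalculation. A relative 8% at about 50% control RFS gives exactly 1.12, and the word increase in the abstract suits a rise in event risk from 50% to 54%. This stands as a possible origin. It does not rescue the text, because neither the relative scale nor the 50% is stated.

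A second reply is that the 8 points may be right and 1.12 may be a different kind of ratio. RFS of 75% against 67% differs by 8 points with a ratio of 0.75/0.67 = 1.12. This also cannot be excluded, but it would mean that the figure labelled a hazard ratio is not one. The statement would still need correcting.

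Third, an abstract is short, the bound is given in full under Sample size, and the natural subject of the remark on clinical considerations is the threshold of 1.12. These are fair points, and both matters are secondary. Even so, the abstract calls 8% the critical value of the margin and gives no other limit.

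Fourth, the effect on the verdict in step 4 assumes that the two hazard ratio criteria decide the trial. They appear under Sample size, while the analysis section lists log-rank and Cox methods at 0.05 without naming them. That assumption should be kept in view. The protocol also states a two-sided 0.05. With 1.96 in place of 1.645 the crossover moves from 88 to about 125 events, which makes the 1.12 criterion matter even less.

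**Conclusion.** The equivalence is wrong as written. On the plain absolute reading it fails at every control rate: 1.12 allows at most 4.17 points, and at assumed control RFS of 40 to 80% the stated 8 is 1.9 to 3.8 times what 1.12 implies. It can be saved only as a relative change at an unstated control RFS near 50%.

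The ceiling rests on proportional hazards alone, which the protocol's hazard ratio criteria and Cox model already presuppose. The other point values depend on the assumed control rates.

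The consequence is for interpretation. The clinical size of the threshold is misdescribed, and the abstract gives a reader no way to see that the confidence limit tolerates roughly 10 to 17 points. Provided both hazard ratio criteria are the decision rule, the verdict would almost never change. This should be fixed. It does not by itself invalidate the design, and it does not judge whether the sample size is sound.

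**What to change.** Keep the pre-set rule as the success criterion: hazard ratio estimate below 1.12 and upper bound below 1.59. From the original derivation, report three things: the assumed control 3-year RFS, whether the 8% was absolute or relative, and whether 1.12 or 8% was the clinical choice.

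Then do one of the following in the Sample size section:

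- Replace the 8% with the absolute difference that 1.12 implies at the assumed rate, for example 4.0 points at 50%.
- Label the 8% as relative, and say whether it is relative to RFS or to event risk.

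If 8 points was the clinical choice, or 1.12 turns out to be another kind of ratio, say so openly and note that the hazard ratio threshold is stricter than intended. Do not loosen it now that, as the abstract puts it, "The study started in 2015 and enrolled 96 patients according to a prior sample size calculation".

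In the abstract, give both hazard ratio criteria with their absolute equivalents at the stated control rate.

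The cost is low: recover the derivation and reword two places. The decision rule does not change.

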## Strengths and limitations of this study

- The proposed study is one of the few randomised trials to compare laparoscopic distal gastrectomy with open distal gastrectomy after neoadjuvant chemotherapy for distal advanced gastric cancer.
- This trial aims to evaluate the efficacy and safety using short-term and long-term endpoints.
- We designed this study to be sufficiently powered to identify non-inferiority in terms of 3-year recurrence-free survival, although it may be underpowered to detect non-difference on other outcomes.
- This is a phase II trial performed at a single medical centre; thus, if the non-inferiority of laparoscopic surgery is proven, a subsequent larger multicentre phase III verification clinical trial may be needed.

cancer in China are already at advanced stage (ie, tumour, node, metastases (TNM) stages II and III) at first hospital visit. The established treatment for advanced gastric cancer is open gastrectomy with D2 lymph node dissection, and postoperative adjuvant chemotherapy of S-1 for 1 year or combination therapy with capecitabine and oxaliplatin for 6 months. Although such a treatment regimen is effective, the prognosis of patients is not satisfactory, which calls for a more intensive chemotherapy. From theoretical perspectives, an intensified chemotherapy can be better tolerated and complied by patients if being administered before the surgery. By far, two large European phase III trials, the Medical Research Council Adjuvant Gastric Infusional Chemotherapy (MAGIC) trial, and the Fédération Nationale des Centres de Lutte contre le Cancer (FNCLCC) and the Fédération Francophone de Cancérologie Digestive (FFCD) 9703 study, have provided supportive evidence that preoperative (neoadjuvant) chemotherapy results in high compliance, as

well as other favourable factors such as high rate of R0 resection and tumour regression, which lead to a better prognosis.

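### The claimed 80% power is unattainable at a true HR of 1: the ceiling is 67% with 80 patients and 71% with 96, even if every patient has an event

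*Protocol*

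**What the plan says.** The protocol's Sample size section sets a two-part rule. On the estimate: "The first criterion was that the HR estimate was smaller than a critical threshold of 1.12". On precision, the "upper estimated one-sided 95% confidence bound of the non-inferiority margin was smaller than 1.59". It then gives the size: "a sample size of 80 (40 per arm) is planned, with a type I error of 0.05 (two-sided) and a statistical power of 80" per cent. For losses it adds: "The total sample size is 96 (48 per arm) after taking account of a 20% dropout rate in each group". The section states no true HR at which the power applies, no control 3-year RFS and no expected number of RFS events.

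The Strengths and limitations box repeats the power claim to readers: "We designed this study to be sufficiently powered to identify non-inferiority in terms of 3-year recurrence-free survival". Data collection and analysis names the analysis sets ("Intention-to-treat and per-protocol approach will be used for efficacy analysis") and gives a level without a side: "All statistical analyses will be conducted in standard statistical software with a significance level of 0.05". The Abstract reports recruitment as done: "The study started in 2015 and enrolled 96 patients according to a prior sample size calculation".

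**The concern.** The variance of a log hazard ratio is set by the number of events. RFS counts one event per patient (first recurrence or death), so 80 patients supply at most 80 events and the intention-to-treat set at most 96. An upper limit on power therefore follows without any assumed RFS, and it lies below the claimed figure.

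Two related faults sit in the same paragraph. A one-sided 95% bound is a one-sided 5% test, yet the error rate is labelled two-sided. The dropout allowance also does not cover the stated 20%.

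The result is meant to inform a phase III trial. If the operations are equally effective, the rule would fail far more often than the 20% that readers are told to expect. A failure could then be read as evidence against laparoscopy when it reflects only too few events.

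**Working it through.** **Inputs from the protocol.** Thresholds 1.12 and 1.59, one-sided 95% bound, type I error 0.05 labelled two-sided, power 80%, 80 patients, 96 after dropout (Sample size); 1:1 allocation (Randomisation and blinding). **Assumption of this check:** true HR = 1, the usual planning value for non-inferiority. The protocol states none.

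**Formula.** With D events and equal arms, SE = 2/√D. Both criteria are met when the log HR estimate lies below min[ln 1.12, ln 1.59 − z·SE], so

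power = Φ( (min[ln 1.12, ln 1.59 − z·SE] − ln HR) / SE ).

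Here ln 1.12 = 0.1133 and ln 1.59 = 0.4637; z = 1.645 for the stated bound and 1.96 for two-sided 0.05.

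**Trying to reproduce 80 patients for 80% power at HR 1.**
- Bound criterion alone: 4(1.645 + 0.8416)²/0.4637² = 115 events; with 1.96, 146. Freedman's formula gives 120 and 152.
- Bound criterion alone at one-sided 0.10, which the protocol does not state: 84 events.
- A binary 8-point margin: at least 174 per arm for control RFS between 50% and 90%.
- Full rule: 4(0.8416)²/0.1133² = 220.6, so about 221 events. The 1.12 limit is binding there, so the answer is the same for either bound.

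None of these gives 80.

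**Ceilings, every patient with an event, HR 1.**
- D = 80: SE = 0.2236; 0.4637 − 1.645 × 0.2236 = 0.0959, below 0.1133, so the bound is the limit. Φ(0.0959/0.2236) = 66.6%.
- D = 96: SE = 0.2041; 0.4637 − 1.645 × 0.2041 = 0.1280, above 0.1133, so 1.12 is the limit. Φ(0.1133/0.2041) = 71.1%.
- With z = 1.96: 54.5% and 62.2%.
- The 1.12 criterion alone, ignoring the bound: 69.4% and 71.1%. So no choice of alpha restores 80%.

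A Cox simulation with every patient having an event gave 65.2% (80 patients) and 70.2% (96), and 79% to 80% at 220 to 222 events.

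**More realistic event numbers.** Control 3-year RFS is assumed, HR = 1, one-sided 95% bound. The last two columns assume exponential times, 2 years of uniform accrual and 3 further years of follow-up.

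| Assumed 3-year RFS | 80 patients, to 3 years: events, power | 96 patients, to 3 years: events, power | 80 patients, 2+3 years: events, power | 96 patients, 2+3 years: events, power |
|---|---|---|---|---|
| 40% | 48, 48.5% | 58, 54.6% | 56, 53.6% | 67, 60.1% |
| 50% | 40, 42.9% | 48, 48.5% | 48, 48.4% | 58, 54.6% |
| 60% | 32, 36.9% | 38, 41.8% | 39, 42.4% | 47, 47.9% |
| 70% | 24, 30.5% | 29, 34.4% | 30, 35.5% | 36, 40.1% |

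With the 97.5% bound and events to 3 years, the same rows give about 36/31/26/21% (80 patients) and 42/36/30/24% (96).

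**True HR that would give 80%** (one-sided 95% bound): 0.912 with 80 events, 0.943 with 96, 0.724 with 40.

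**Dropout.** 80 × 1.2 = 96, which covers 1 − 80/96 = 16.7% loss. At 20% loss, 96 × 0.8 = 76.8 remain, and 80/0.8 = 100 would be needed to keep 80.

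**The case against.** **HR 1 is not the protocol's assumption.** This is true, and 80% is attainable if laparoscopy is truly better: HR about 0.91 if all 80 patients have events. But the protocol states no such benefit, and its Introduction describes survival after the two approaches as comparable. Power with no stated alternative cannot be checked, which is part of the fault. The cited design paper and prior studies are not at hand, so an unprinted assumption cannot be excluded.

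**The 221 depends on 1.12, which the same section equates with an 8-point RFS difference.** This stands as a qualification. Under proportional hazards an HR of 1.12 gives at most 4.2 points (the maximum of S − S^1.12). An 8-point loss from an assumed control RFS of 40/50/60/70% is an HR of about 1.24/1.25/1.28/1.34. If that were the intended threshold, the bound would bind, the full rule would need about 115 events, and the 96-event ceiling would be 73%. The 67% at 80 events would not change. Either way 80% is out of reach at HR 1.

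**Relabelling alpha as one-sided picks the more lenient level after enrolment in an open-label trial.** The stated decision bound is already one-sided 95%, so the relabelling follows the rule as written. The sponsor should still confirm which level was planned.

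**The dropout point is small.** Agreed. In an intention-to-treat survival analysis, dropouts are censored and still contribute follow-up, so the 77 are patients with complete follow-up and not the whole analysis set.

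**It is a single-centre phase II trial that already foresees phase III.** This limits the harm, but nothing in the document corrects the claim of sufficient power for its primary endpoint.

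**Conclusion.** The concern holds and must be fixed. Given a true HR of 1 and the rule as printed, the chance of missing it is at least 33% with 80 patients and 29% with 96, against the 20% implied. These minima assume that every patient has an event, so they need no assumed RFS. Over the assumed control RFS range of 40% to 70%, with events counted to 3 years, the chance of missing is about 52% to 69% with 80 patients and 45% to 66% with 96. The figure of 221 events depends on 1.12 being the intended threshold; the 67% ceiling does not. The mismatch between the two-sided label and the one-sided bound is also real: at the ceilings it shifts power by 12 points (80 events) or 9 points (96). The dropout arithmetic is a minor error of four patients.

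**What to change.** In Sample size:
- State the assumed true HR, the control 3-year RFS and the expected number of RFS events.
- Label the type I error one-sided 5%, to match the stated bound. If the sponsor had planned a 97.5% bound, the bound must change instead, and the ceilings are then 55% and 62%.
- Replace 80% with the power of the full two-part rule under those assumptions at that level. At HR 1 with 80 patients it cannot exceed 67%.
- Reconcile 1.12 with the 8-point difference before recomputing, since the 96-patient ceiling and the event requirement depend on it.
- State that 96 patients leave about 77 with complete follow-up at 20% dropout.

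In Data collection and analysis, give the same one-sided level for the primary non-inferiority analysis. In Strengths and limitations, withdraw the claim of sufficient power. Add that failing the rule, on the 1.59 bound or on the 1.12 estimate, is inconclusive and not in itself evidence of inferiority.

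The cost is a less favourable power statement. Since the Abstract reports all 96 patients enrolled, only text changes: no extra patients, visits or procedures.
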